8.1.1.3. Non-inferiority on RVNA Response Rate

The third element is immune response to the rabies vaccine on Study Day 99 measured by the noninferiority percent of the study population RVNA ≥ 0.5 IU/mL SYN023 vs HRIG. This approach assesses the noninferiority of the percent of subjects who have a serum RVNA concentration that is generally recognized as protective, the more important measure of vaccine compatibility.

The alternative hypothesis (H_a) is that the response rate in SYN023 vaccine (r_{SYN023}) is non-inferior to HRIG (r_{HRIG}) by a 20% margin (0.8 in terms of a ratio). Given that the statistics can be defined as the rate ratio $\emptyset = \frac{r_{SYN023}}{r_{HRIG}}$, the alternative hypothesis can be written as:

$$H_a: \emptyset = \frac{r_{SYN023}}{r_{HRIG}} > 0.8$$

and the null hypothesis as:

$$H_0: \emptyset = \frac{r_{SYN023}}{r_{HRIG}} \leq 0.8.$$

As the rate ratio \emptyset and the rate difference $\Delta = r_{SYN023} - r_{HRIG}$ are interchangeable with log transformation, it is equivalent to test on the test statistic Δ with Pearson's chi-square test or, in case of small sample sizes (responders in either group is less than 5 subjects), Fisher's exact test. This can be achieved by using SAS procedure FREQ (use the option *riskdiff* and additional option *Newcombe* with the *tables* statement). In the summary table, by-treatment risk rates with corresponding SDs, risk ratio and the asymptotic CI for the risk ratio based on the Wilson score method will be back transformed and displayed. In case of small sample sizes, an exact CI based on the Clopper-Pearson method will be presented instead. The null hypothesis will be rejected at a significance level of 2.5% ($\alpha = 0.025$) if the lower bound of the two-sided 95% CI for the risk ratio is greater than the non-inferiority bound 0.8.

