3.9.2 Pharmacodynamic Efficacy Evaluations

The serum RVNA ≥ 0.5 IU/mL for the 365 day trial duration is the pharmacodynamic efficacy parameter. These specimens will be collected and forwarded to the study laboratory at the University of Kansas. These measurements will be used to calculate both superiority for Study Day 8 GMC RVNA and non-inferiority for Study Day 99 GMC RVNA and % population RVNA ≥ 0.5 IU/mL. A missing RVNA datapoint or RVNA data point less than 0.5 IU/mL preceded and followed by RVNA concentrations ≥ 0.5 IU/mL will be considered to be in the protective range.

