Non-Inferiority test for ratio of two proportions is used for determining the sample size. The null hypothesis is that the ratio for the two treatments is less than the defined margin which is expressed as:

$$H_0: \emptyset \leq \emptyset_L \text{ where } \emptyset_L < 1$$

The sample size is estimated for an 80% power of demonstrating noninferiority of a 20% margin of non-inferiority and equal allowance (number of subjects in group 1 = number of subjects in group 2) with a p value = 0.025 (Table 7.8.3-2).

7.8.3-2 Noninferiority Sample Size and Percentage of Subjects with RVNA ≥ 0.05 IU/mL

Assumed SYN023 Proportion	Assumed HRIG Proportion	Margin	Total Sample Size
1	1	0.2	32
1	1	0.1	72

Samples sizes are shown for noninferiority for two proportions using a 20% margin that requires a total of 32 and a 10% margin that requires a total sample of 72 both of which can be demonstrated with the current 368 subject sample.

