2.1. Primary Objective

The primary objective is a composite endpoint with four elements:

- To demonstrate that the geometric mean rabies virus neutralizing activity (RVNA) concentration for SYN023 recipients is superior to the geometric mean RVNA concentration for human rabies immune globulin (HRIG) recipients on Study Day 8 AND
- To demonstrate that the Study Day 99 geometric mean RVNA concentration for SYN023 recipients is not inferior to the geometric mean RVNA concentration for HRIG recipients AND
- To demonstrate that the percentage of subjects with RVNA concentration ≥ 0.5 IU/mL on Study Day 99 in SYN023 recipients is not inferior to the percentage of recipients with RVNA concentration ≥ 0.5 IU/mL for HRIG AND
- There are no cases of probable or confirmed rabies in SYN023 recipients.

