- baseline will be defined as the last non-missing assessment prior to the first dose date (and time, if available on Study Day 1).
- Change from baseline is defined as: post-baseline value – baseline value.

The Study Day will be calculated as follows:

- If the assessment date occurs on or after the date of the first dose of study drug:
Study Day = assessment date – first dose date + 1.
- If the date of interest occurs before the date of the first dose of study drug:
Study Day = assessment date – first dose date
- There is no Study Day 0.

Missing data will not be imputed except for incomplete or partial dates of adverse events (AEs) and concomitant medications. Imputation rules for such will be described in the corresponding sections.

By timepoint summaries will be based on case report form (CRF) visits. For efficacy analyses, unscheduled results will not be considered but only be listed in by-subject listings. For safety analyses, unscheduled results will not be presented in by-timepoint summaries. However, it will be considered for overall post-treatment maximum or minimum values when reporting safety abnormalities.

All analyses will be conducted using SAS Version 9.4 or higher. If not pre-specified, statistical tests will be two-sided and interpreted at a 5% significance level.

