8.1.1. Primary Analysis

8.1.1.1. Superiority Testing on Study Day 8

The first element is superiority of the geometric mean concentration of RVNA (serum) in SYN023 recipients on Study Day 8. RVNA was selected because it is a generally accepted surrogate for rabies vaccine protection. If it is possible to demonstrate quicker and higher concentrations in the blood of RVNA from SYN023 then this may be evidence of greater potency and perhaps effectiveness.

GMC for a group of subjects is calculated by multiplying all values and taking the n th root of this number, where n is the number of subjects with available data. Because concentrations are often approximately log-normally distributed, they are customarily analyzed on a logarithmic (log) scale; a difference in arithmetic means (Δ) on a log scale becomes a ratio of geometric means (\emptyset) when the results of analysis are converted back to the original data scale. Thus, each hypothesis is a statement regarding \emptyset . The alternative hypothesis (H_a) is that the SYN023 vaccine is superior to HRIG.

$$H_a: \emptyset = \frac{GMC_{SYN023}}{GMC_{HRIG}} > 1$$

The null hypothesis is the complement of the alternative, meaning that the SYN023 vaccine is inferior or equal to HRIG.

$$H_0: \emptyset = \frac{GMC_{SYN023}}{GMC_{HRIG}} \leq 1$$

The null hypothesis will be rejected at a significance level of 2.5% ($\alpha = 0.025$) if the lower bound of the one-sided 97.5% confidence interval (CI) for the GMC ratio is greater than 1.

In the summary table, by-treatment GMCs and geometric standard deviations (Geo SDs) will be displayed, where Geo SD is calculated by converting the normal concentration values in to log-normal values, calculating the typical standard deviation of log transformed concentrations and then taking its antilog for the geometric standard deviation. GM ratio along with its coefficient of variation (CV) and 95% CI will also be displayed in the summary table.

8.1.1.2. Non-inferiority Testing on Study Day 99

The second element is immune response to the rabies vaccine on Study Day 99 measured by the noninferiority of the Study Day 99 GMC of RVNA in SYN023 recipients compared to Study Day 99 GMC of RVNA in the HRIG recipients. Synermore defines non-inferiority rabies vaccine response as a 20% margin of non-inferiority and equal allowance (number of subjects in SYN023 = number of subjects in HRIG) and alpha is taken to be 0.025.

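### The Day 99 responder-rate test is stated on the ratio but computed on the raw difference; if that interval is exponentiated, this element's type I error is about 10% to 11%, not 2.5%

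*SAP*

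**What the plan says.** The percentage of subjects at or above 0.5 IU/mL on Study Day 99 is one of the four elements that must all be met (SAP 2.1: "The primary objective is a composite endpoint with four elements"). SAP 8.1.1.3 sets the null hypothesis as r_SYN023 / r_HRIG ≤ 0.8. Protocol 7.8.3 plans on the same scale: "Non-Inferiority test for ratio of two proportions is used for determining the sample size".

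SAP 8.1.1.3 then defines a difference Δ = r_SYN023 − r_HRIG on the raw rates and states that the ratio and Δ "are interchangeable with log transformation, it is equivalent to test on the test statistic" Δ. It names the Pearson chi-square test (Fisher's exact test for small counts) and the SAS FREQ options riskdiff and Newcombe. On output, the "asymptotic CI for the risk ratio based on the Wilson score method will be back transformed and displayed". The null is rejected "if the lower bound of the two-sided 95% CI for the risk ratio is greater than the non-inferiority bound 0.8".

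On who counts as a responder, Protocol 3.9.2 treats a missing value in the same way as a low one: an "RVNA data point less than 0.5 IU/mL preceded and followed by RVNA concentrations ≥ 0.5 IU/mL will be considered to be in the protective range". SAP Section 4 says "Missing data will not be imputed except for incomplete or partial dates of adverse events (AEs) and concomitant medications", and SAP 11.1 drops missing concentrations from the calculation.

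**The concern.** The identity is log(r1/r2) = log r1 − log r2. It says nothing about r1 − r2. SAP 8.1.1.1 uses the valid form for concentrations, where a difference in means "on a log scale becomes a ratio of geometric means". Section 8.1.1.3 carries that step over to proportions that are never logged. Riskdiff with Newcombe yields an interval for the difference, and no formula turns it into an interval for the ratio. Three programs could claim to follow the text:

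- **A.** Exponentiate the Newcombe limits and compare with 0.8. This is the natural reading, since the SAP's back-conversion elsewhere (8.1.1.1, 15.2) is the antilog.
- **B.** Compare the Newcombe lower limit with −0.20.
- **C.** Ignore riskdiff and compute an interval for the ratio.

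At stake is whether a primary element has one pre-specified decision rule at its stated one-sided 2.5%.

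**Working it through.** **Inputs.** One-sided α 0.025, bound 0.8 (SAP 8.1.1.3). 320 per-protocol subjects, 1:1, so 160 per arm (SAP 4.1, 3.1.6). HRIG response 100% (planning value, Protocol Table 7.8.3-2) and 75/76 = 98.7% (historical Day 112, Table 7.8.3-1). HRIG 95% and 90% are assumptions of this review, added to show the trend.

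**The protocol's own figure.** Protocol 7.8.3 gives totals of 32 (20% margin) and 72 (10% margin) with both rates at 1. For a score test of the ratio with every subject responding, z = (1 − φ) / √(φ(1 − φ)/n).
- φ = 0.8: z = 0.5√n ≥ 1.96 gives 16 per arm, total 32.
- φ = 0.9: z = √n/3 ≥ 1.96 gives 35 per arm, total 70; the Miettinen-Nurminen variance factor raises this to 36 per arm, total 72.

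The stated sizes reproduce. They do not settle the scale, because at HRIG 100% a ratio of 0.8 and a difference of −0.20 are the same point.

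**Margin implied by reading A.** The cut-off on the difference is ln 0.8 = −0.2231, whereas the null boundary is −0.2 × r_HRIG. The effective ratio margin is 1 + ln(0.8)/r_HRIG: 1 − 0.2231 = 0.777 at HRIG 100%, and 1 − 0.2231/0.987 = 0.774 at 98.7%.

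**Type I error of this element alone.** Full enumeration of both binomials, 160 per arm, r_SYN023 = 0.8 × r_HRIG:

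| Rule | HRIG 100% | 98.7% | 95% (assumed) | 90% (assumed) |
|---|---|---|---|---|
| A: exp(Newcombe limit) > 0.8 | 9.7% | 10.9% | 14.1% | 17.9% |
| B: Newcombe limit > −0.20 | 2.6% | 2.8% | 4.7% | 7.1% |
| C: Miettinen-Nurminen ratio | 2.6% | 2.1% | 2.2% | 2.3% |
| C: Wilson-based MOVER ratio | 2.6% | 2.4% | 2.6% | 2.6% |
| C: log-ratio Wald | 4.3% | 4.1% | 3.5% | 3.0% |

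Farrington-Manning agrees with Miettinen-Nurminen to within 0.1 point. At 184 per arm, rule A gives 8.7% (HRIG 100%) and 11.5% (98.7%), so full enrolment does not remove the problem.

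**Example.** HRIG 158/160 = 0.9875 (Wilson upper limit 0.9966); SYN023 133/160 = 0.8313 (Wilson lower limit 0.7656).
- Ratio: 133/158 = 0.842.
- Newcombe lower limit: (0.8313 − 0.9875) − √((0.8313 − 0.7656)² + (0.9966 − 0.9875)²) = −0.2225.
- exp(−0.2225) = 0.8005, so rule A passes.
- Lower limit for the ratio itself: 0.774 (Miettinen-Nurminen) or 0.775 (MOVER), so rule C fails.

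With 158/160 on HRIG, rule A passes from 133 SYN023 responders; rule B and the score and MOVER ratio intervals pass from 137.

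**Joint with the Day 99 GMC element.** Assume log-normal RVNA. The log SD from the Day 112 intervals in Protocol Table 7.8.2-1 is ln(U/L)/2 × √n / t:
- SYN023: ln(1.87/1.09)/2 × √73/1.993 = 1.16.
- HRIG: ln(2.11/1.38)/2 × √76/1.992 = 0.93.

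With either value as a common SD σ, the GMC ratio at the responder boundary is exp{σ[Φ⁻¹(0.8 r_HRIG) − Φ⁻¹(r_HRIG)]}. This is 0.19 to 0.52 for HRIG rates of 98.7% down to 90%, far below 0.8. In 20,000 simulated trials per scenario (HRIG 98.7%, 95%, 90%), both elements passed in none. HRIG at exactly 100% cannot be represented by a log-normal.

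**At the historical rates** (95.9% v 98.7%, Day 112), the readings disagree with probability below 0.0001%.

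**The case against.** The strongest reply is that SAP 8.1.1.3 does state a rule, namely a risk-ratio interval with lower limit above 0.8. Only the route is unclear, and the SAP never says outright to exponentiate a raw difference. This is partly right: the 10% to 11% is conditional on reading A. But a primary-element test whose error is 2.6% or 10.9% depending on the programmer is not pre-specified, and the equivalence sentence is wrong under every reading.

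Second, the window is narrow: 133 to 136 SYN023 responders with HRIG 158/160, or 135 to 137 with HRIG 160/160. Historical SYN023 rates were 100% (Day 84) and 95.9% (Day 112), and even at a true 92% the readings disagree only about 0.25% of the time. This stands and limits the practical effect. However, Protocol 5.1.5.3 opens the NRG with as few as 75% of SYN023 recipients in range on Day 99, so 83%–86% is not outside what the protocol contemplates.

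Third, all four elements must pass, and the GMC element blocks false overall success. This stands under the log-normal assumption, so no inflation of the trial-wide error is claimed.

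Fourth, the Fisher and Clopper-Pearson fallback applies only below 5 responders, which will not arise at these sample sizes. It is a minor point: chi-square and Fisher test equality rather than a 0.8 margin, and Clopper-Pearson is a one-proportion interval.

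Fifth, the responder definition is a separate matter, and the Section 3.9.2 rule is the one cited for the DSMB reviews. It is separate, but Protocol 3.9.2 itself applies these measurements to the Day 99 percentage, so the conflict reaches the primary analysis. Its effect has not been quantified.

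**Conclusion.** The concern holds and should be fixed before unblinding. SAP 8.1.1.3 rests a primary element on a false equivalence and leaves its interval undefined. On the natural reading, the element's type I error is 9.7% to 10.9% at 160 per arm and the HRIG rates in the documents, against a stated 2.5%; a direct score or MOVER interval for the ratio gives 2.1% to 2.6%. The figure applies to this element alone and depends on exponentiating the Newcombe limits. At the expected response rates the conclusion would be the same under every reading. The Day 99 responder is also defined in conflicting ways in the protocol and the SAP.

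**What to change.** In SAP 8.1.1.3, delete the equivalence sentence, the chi-square and Fisher tests and the Clopper-Pearson fallback. Specify a two-sided 95% interval computed directly for the risk ratio at all counts, either a score interval (Miettinen-Nurminen or Farrington-Manning) or the Wilson-based MOVER ratio interval, and require its lower limit to exceed 0.8. Name one method only.

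While editing, align Protocol Table 7.8-1, which lists a 10% margin for this element, with the 20% used in the protocol rationale and SAP 8.1.1.3.

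Separately, reconcile Protocol 3.9.2 with SAP Section 4 and 11.1 so that one definition applies. Since the objective is the percentage at or above 0.5 IU/mL on Study Day 99, a measured Day 99 value below 0.5 should count as a non-response, and one stated rule should cover missing Day 99 values.

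The cost is one SAP paragraph, one line of code, one protocol sentence and a table entry. Sample size and data collection are unaffected.

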8.1.1.4. Probable or Confirmed Cases of Rabies

The fourth element is the absence of probable or confirmed cases of clinical rabies in the SYN023 recipients. Synermore estimates this possibility of rabies at approximately 0.1% to

0.01%. This means there is a small chance of a single case of confirmed rabies occurs in the 184 subjects in the SYN023 NRG group.

Study drug administration will be paused for DSMB confirmation of rabies diagnosis and review. Unblinded data will be presented to the DSMB during the closed sessions. If a confirmed case of rabies occurs in the per-protocol SYN023 group, the DSMB will issue a written communication to permanently stop study enrollment and study drug administration. A descriptive summary table with counts of cases will be prepared after receiving DSMB confirmation for the end of study report after database lock and unblinding.

8.1.2. Sensitivity Analyses

The as-treated analyses will be performed for the four elements of the primary analysis as the sensitivity analyses.

8.2. Secondary Efficacy Endpoints

The below secondary efficacy analyses will be performed on the Per-protocol Population for the NRG group. Descriptive statistics will be displayed in a summary table following the same presentation for Section 8.1.1.1.

- To test that the GMC of RVNA in the SYN023 group is superior to the GMC of RVNA in the HRIG group on Study Day 4.
- To test that the GM ratio of RVNA AUEC₁₋₁₅ for SYN023 to HRIG is superior.

The below secondary efficacy analyses will be performed on the As-treated Population and the Per-protocol for the LRG and NRG, separately. Descriptive statistics will be displayed in a summary table following the same presentation for Sections 8.1.1.1 and 8.1.1.3; however, hypothesis testing will not be performed.

- By-treatment GMT ratio of RVNA at each time point
- By-treatment response rate (RVNA ≥ 0.5 IU/mL) at each time point

Subjects with increased BMI or not will be presented with RVNA concentrations over time for the two risk groups based on the As-treated and Per-protocol Populations in SYN023 recipients.

Any probable or confirmed rabies case that is identified in subjects with SYN023 administered within 54 hours of rabies exposure will be reported following the summary for Section 8.1.1.4.

9. Safety Analysis

Safety evaluations include adverse events, clinical laboratory, vital signs and physical examination assessments. Safety analyses will be performed using the As-treated Population. Summaries will be presented by risk group (LRG and NRG) and treatment group (SYN023, HRIG and overall). The safety profile of study drug will be described by treatment group.

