Subjects who are discovered to not have satisfied any criteria for the per-protocol population may be excluded from that population by the Per Protocol Adjudication Board. Any exclusion of

randomized subjects from the per-protocol population after randomization must be made by the Per Protocol Adjudication Board (Section 3.2.8).

ANALYSIS OF EFFICACY

The absence of a confirmed or probable case of rabies in the per-protocol population is part of the composite endpoint (3.9.1). Subject will be periodically evaluated for the clinical signs and symptoms of human rabies. If these develop they will be referred for medical evaluation and laboratory or anatomic confirmation. All clinical rabies diagnostic tests may be performed locally at a qualified laboratory. All rabies cases will be reviewed by the DSMB.

The primary pharmacodynamic efficacy parameter is a composite endpoint with the following elements (see Section 2.1):

- the superiority of RVNA GMC RVNA on Study Day 8 in SYN-23 recipients compared. This represents early anti-rabies activity
- the noninferiority of Study Day 99 GMC RVNA in SYN023 recipients vs HRIG recipients. This represents the immune response to rabies vaccination.
- the noninferiority of the Study Day 99 percentage of SYN023 recipients with RVNA \geq 0.5 IU/mL compared to HRIG recipients.

The criteria for a probable or definite (confirmed) rabies case in Sections 3.9.1 and 7.8.4. The criteria for superiority for Study Day 8 GMC RVNA are described in Section 7.3 and 7.8.1. The criteria for non-inferiority of the Study Day 99 GMC RVNA and percentage of the group with RVNA \geq 0.5 IU/mL are described in Section 7.3, 7.8.2 and 7.8.3.

Analyses of efficacy will be performed on the per-protocol and as-treated populations for each risk group.

All pharmacokinetic analyses of serum SYN023 concentrations will be done on the per-protocol and as treated populations. Individual analyses will be performed and descriptive statistics will be used to describe the results of individual analyses. PK parameters for SYN023 Mab will be estimated using non-compartmental analysis. Vd, C_{max}, T_{max}, AUC_{0-t}, AUC_{0-inf}, t_{1/2}, Cl, and λ_z will be calculated when possible. Effect of BMI on pharmacodynamic and pharmacokinetic parameters will be performed.

ANALYSIS OF ANTI-DRUG ANTIBODY

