- The fourth element is the absence of probable or confirmed cases of clinical rabies in the SYN023 recipients (Section 3.9.1). There is no need to specify "suspected" cases of rabies since entry into the protocol requires exposure to a possibly rabid animal and this is the factor that makes a case "probable" as opposed to "suspected." It is likely that there will no cases of rabies in the per protocol population of either treatment arm therefore a non-inferiority test could not be done. Synermore estimates the failure rate of properly administered PEP in adults to be between 1 in 1000 and 1 in 10,000 (Hemachudha et al. 1999, Hampson et al. 2008, Quiambao et al. 2008, Quiambao et al. 2009 Shantavasinkul et al. 2010, Wilde et al. 2007). A single case of rabies in a subject properly treated with PEP meeting the per-protocol conditions in a 160 subject sample of adults would be an occurrence rate of 0.63% and the 95% confidence interval extends from 0 to 2%. This rate of failure would be evidence for a lack of effectiveness.

7.4 Secondary Objectives: Clinical and Pharmacodynamic Efficacy.

To demonstrate that the proportion of SYN023 recipients with blood RVNA concentrations that meet the generally accepted as adequate threshold ≥ 0.5 IU/mL, for Study Days 8-99 in the per-protocol population is not inferior to the same proportion in HRIG recipients. A similar analysis will be performed for the as-treated population for sensitivity analysis.

To demonstrate that SYN023 administered within 54 hours of rabies exposure with rabies vaccinations prevents all probable or confirmed clinical rabies cases.

To describe the ratio of the geometric mean concentrations of RVNA at each time point in SYN023 recipients divided by the geometric mean concentrations of RVNA in HRIG recipients for the per-protocol and as-treated populations for each risk group.

To describe ant effect of increasing BMI on RVNA concentrations.

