2.2. Secondary Objective(s)

- To demonstrate that the geometric mean RVNA concentration for SYN023 is superior to the geometric mean RVNA concentration for HRIG on Study Day 4.
- To demonstrate that the geometric mean RVNA AUEC₁₋₁₅ for SYN023 is superior to the geometric mean RVNA AUEC₁₋₁₅ for HRIG
- To describe the ratio of the geometric mean concentrations of RVNA at each time point in SYN023 recipients divided by the geometric mean concentrations of RVNA in HRIG recipients for LRG and NRG in the Per-protocol and As-treated Populations.
- To describe the percentage of RVNA concentration ≥ 0.5 IU/mL at each time point for SYN023 and HRIG recipients for LRG and NRG in the Per-protocol and As-treated Populations.
- To describe the pharmacokinetics of SYN023 using non-compartmental analysis. V_d , C_{max} , T_{max} , AUC_{1-t} , AUC_{1-inf} , $t_{1/2}$, Cl , and λ_z will be calculated when possible in the LRG and NRG Per-protocol and As-treated Populations.

- To evaluate presence and effects of anti-SYN023 antibodies (anti-CTB011, anti-CTB012).
- To evaluate the safety of SYN023 compared to HyperRab® S/D.
- To describe any effect of increasing BMI on SYN023 and RVNA concentrations.

3. Investigational Plan

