6.1. Demographics

Demographics for all subjects in the As-treated Population will be presented in a listing. Listings of randomized subjects who missed any dose of study drug or rabies vaccine and of subjects with protocol deviations will be provided.

The age and body mass index (BMI) collected in CRF will be used for analysis if it is non-missing. If the age is not collected in the CRF, the age in years is calculated using the date of the informed consent and date of birth.

Age (years) = [(Informed Consent Date – Date of Birth + 1) / 365.25].

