10.2. Pharmacokinetic Concentrations

Blood samples will be obtained during the course of the study for use in determining the PK concentrations of CTB011 and CTB012 in serum. These will be collected before administration of study drug on Study Day 1 for all subjects, then on Study Days 4, 8, 15, 29, 43, 71, 127, 155, 183 and 274 for the LRG; and on Study Days 4, 8, 15 and 99 for the NRG.

Individual serum concentrations of CTB011 and CTB012 will be presented in the data listings and summarized by nominal time point for ease of presentation using descriptive statistics (n , mean, SD, CV, min, median, and max), by ADA status, and also by Per-protocol (LRG and NRG) and As-treated Populations. The mean serum concentrations of CTB011 and CTB012 will be plotted versus nominal collection time, and the individual serum concentration of CTB011 and CTB012 will be plotted versus actual collection time on both linear and semilogarithmic scales, by ADA status.

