10.3. Pharmacokinetic Parameters

The serum concentration-time data for CTB011 and CTB012 will be analyzed by non-compartmental analysis using WinNonlin Phoenix Version 8.0 or higher. For PK analysis, actual sampling times and actual doses administered will be used. For the calculation of PK parameters, all serum concentrations that are BLQ prior to the first measurable concentration will be set to zero. The BLQ values that are between measurable concentrations will be set to missing. The BLQ values that occur at the end of the profile after the last quantifiable concentration will be set to missing.

If data allow, the following PK parameters will be derived from the individual serum concentrations of CTB011 and CTB012 over time profile using non-compartmental methods:

AUC _{1-t}	Area under the serum concentration-time curve from time 0 on Study Day 1 to the last quantifiable concentration, calculated using the linear trapezoidal linear interpolation rule
AUC _{1-inf}	Area under the serum concentration-time curve from time 0 on Study Day 1 extrapolated to infinity, calculated using the formula: AUC _{1-inf} = AUC _{1-t} + [C _t / λ _z], where C _t is the last measurable serum concentration and λ _z is the terminal elimination rate constant. If the extrapolated area (C _t /λ _z) is greater than 20% of AUC _{1-inf} , then AUC _{1-inf} and its associated parameters (CL/F and Vd/F) will be set to missing.
C _{max}	Maximum observed serum concentration
T _{max}	Time of maximum observed serum concentration
λ _z	Terminal elimination rate constant, where λ _z is the magnitude of the slope of the linear regression of the log concentration versus time profile during the terminal phase. λ _z will only be retained if R ² ≥ 0.80 and 3 points in the terminal phase that do not include C _{max} are included in determining the regression line.
t _{1/2}	Terminal half-life (whenever possible), calculated as ln(2)/λ _z
CL/F	Apparent clearance, calculated as Dose/AUC _{1-inf}
Vd/F	Apparent volume of distribution, calculated as (CL/F)/λ _z

Individual serum PK parameters of CTB011 and CTB012 will be presented in the data listings. Further, CTB011 and CTB012 PK parameters will be summarized using descriptive statistics (n, mean, SD, CV, min, median, and max) by ADA status, and also by Per-protocol (LRG and NRG) and As-treated Populations.

11. Pharmacodynamics

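### The BMI objective names SYN023 and RVNA concentrations, but the SAP plans only an RVNA display by an undefined BMI split and no BMI analysis of CTB011/CTB012

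*SAP*

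**What the plan says.** The objective has the same two outcomes in Protocol 2.1 and SAP 2.2: "To describe any effect of increasing BMI on SYN023 and RVNA concentrations". The protocol synopsis, under its analysis of efficacy, goes further: "Effect of BMI on pharmacodynamic and pharmacokinetic parameters will be performed".

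The analysis text is narrower. Protocol 7.4 has "To describe ant effect of increasing BMI on RVNA concentrations", and Protocol 7.5, on pharmacokinetics, does not mention BMI. SAP 8.2 has one sentence: "Subjects with increased BMI or not will be presented with RVNA concentrations over time for the two risk groups", continuing "based on the As-treated and Per-protocol Populations in SYN023 recipients".

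For the drug itself, SAP 10.2 groups serum CTB011 and CTB012 concentrations "by ADA status, and also by Per-protocol (LRG and NRG) and As-treated Populations". In SAP 10.3, "CTB011 and CTB012 PK parameters will be summarized using descriptive statistics", with the same groupings. BMI appears in neither section.

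On the covariate, SAP 6.1 says only "The age and body mass index (BMI) collected in CRF will be used for analysis if it is non-missing". It gives no threshold or categories. SAP Section 14 declares no changes to the planned analysis.

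**The concern.** There are two gaps. First, one of the two named outcomes, drug concentration, has no analysis by BMI. SYN023 is dosed by body weight, so how serum concentration varies with body size is a natural exposure question. RVNA answers it only in part, because the assay also picks up vaccine-induced antibody.

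Second, the RVNA display cannot be programmed as written. Increased could mean above some baseline threshold or a rise during follow-up. Placing BMI among the demographics in SAP 6.1 suggests a baseline value, but the SAP does not say so. If no cut-off is fixed in advance, someone will choose it later, possibly with the data in view. Even with a cut-off, a two-group contrast is a blunt way to describe the effect of a covariate that increases continuously.

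**Working it through.** **Text check.** The statements on BMI, side by side:

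| Place | SYN023 (CTB011/CTB012) | RVNA |
|---|---|---|
| Protocol 2.1 and SAP 2.2, objective | yes | yes |
| Protocol synopsis, analysis of efficacy | yes (PK parameters) | yes (PD parameters) |
| Protocol 7.4 | no | yes |
| Protocol 7.5 | BMI not mentioned | not applicable |
| SAP 8.2 | no | yes, two undefined groups, SYN023 recipients only |
| SAP 10.2 and 10.3 | summarised, but not by BMI | not applicable |

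The objective and synopsis promise two outcomes, and the analysis sections deliver one. The mismatch starts inside the protocol, between the synopsis and Sections 7.4 and 7.5. The SAP repeats it without comment.

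**Can RVNA stand in for drug concentration?** Protocol Table 7.8.3-1 gives earlier-study results. Its days are counted from 0, so Day 7 is Study Day 8 and Day 14 is Study Day 15.

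- Day 7, at or above 0.5 IU/mL: 75/75 on SYN023 and 6/76 (7.9%) on RIG. In SYN023 recipients, RVNA at this point is largely drug.
- Day 14: 75/75 on SYN023 and 75/76 (98.7%) on RIG. By then vaccine response alone could account for the result.

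RVNA is therefore an indirect guide to exposure at Study Days 4 and 8, and a poor one from Study Day 15.

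**Size of the loss from splitting BMI (illustration only).** The documents give no sample size, effect size or power for this objective, so there is no figure to reproduce. Assume BMI is roughly normal, its relation to log concentration is linear, and a share p of subjects lies above cut-off c. The efficiency of the split relative to a linear term is

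E = φ(c)² / [p(1 − p)].

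At p = 0.5, c = 0 and φ(0) = 0.3989, so E = 0.1592/0.25 = 0.637 (that is, 2/π). The documents do not give p, so a range is shown. Effective n is n × E, with n = 160 for NRG per-protocol SYN023 recipients (half of the 320 in SAP 4.1) and n = 45 for the LRG maximum (SAP 4.1).

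| p above cut-off | E | Loss | Effective n of 160 | Effective n of 45 |
|---|---|---|---|---|
| 50% | 0.637 | 36% | 102 | 29 |
| 30% | 0.576 | 42% | 92 | 26 |
| 20% | 0.490 | 51% | 78 | 22 |
| 10% | 0.342 | 66% | 55 | 15 |

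**Which days can carry a log-scale drug model?** SAP 10.2 samples the NRG before dosing on Day 1 and then on Days 4, 8, 15 and 99. Day 1 is pre-dose. The protocol's rationale for pregnancy avoidance states that SYN023 can no longer be detected by Day 99. SAP 10.1 sets values below quantification to zero for descriptive statistics, and the log of zero is undefined. That leaves Days 4, 8 and 15.

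This also limits the NRG PK parameters. SAP 10.3 keeps the terminal rate constant only with 3 terminal points that exclude Cmax. If Day 99 is below quantification, 3 post-dose values remain; removing Cmax leaves 2. Half-life, clearance, volume and AUC to infinity would then not be estimable in the NRG. Cmax and AUC to the last quantifiable value would be.

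**The case against.** The strongest reply is that this is a descriptive secondary objective. No BMI test, slope or power is planned. A display of RVNA in higher- and lower-BMI subjects shows direction and rough size, and early RVNA in SYN023 recipients already reflects the drug. The SAP also follows Protocol 7.4 as written.

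Much of this stands. A reader might infer that a two-group display cannot describe a BMI effect at all. That goes too far: it gives a crude contrast, though not a gradient. A reader might also infer that the trial loses a third or more of its sample for this question. The documents do not support that either: they specify no median split, no normality and no linear model, so the efficiency figures only illustrate what splitting can cost. Nor do the documents show that the SAP alone dropped the pharmacokinetic part, since Protocol 7.4 had already narrowed the item.

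The reply does not supply the missing analysis. Early RVNA is a proxy for two visits, whereas the objective and synopsis name the drug outcome directly. Descriptive status does not settle an undefined grouping.

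**Conclusion.** The point holds as a gap between a stated objective and its analysis. CTB011 and CTB012 are not analysed by BMI anywhere in the SAP, although the objective and the protocol synopsis call for it. RVNA is shown only by a split that nobody has defined. That conclusion rests on the text alone and needs no distributional assumption.

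The consequence is limited. The objective is secondary and descriptive, and no primary conclusion depends on it. A reader might take the data to be lost. They are not: BMI and the concentrations are planned for collection, so the analysis can be specified now. The exposure argument from weight-based dosing is an inference, since the documents give no reason for including the BMI objective. The 36% to 66% loss over splits from 50% to 10% above the cut-off holds only under normal BMI and a linear relation.

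**What to change.** 1. In SAP 8.2 and Section 10, for SYN023 recipients by risk group, describe log RVNA and log CTB011 and CTB012 concentrations against continuous baseline BMI: log C = α + β × BMI at each chosen day. Report the ratio per 5 kg/m², exp(5β), with its 95% CI. Treat PK parameters the same way where they can be estimated.
2. Limit the drug-concentration models to post-dose days with mostly quantifiable values, for example Days 4, 8 and 15 in the NRG. In the LRG, name the days explicitly, because the later sampling days in Protocol Table 3-1 and SAP 10.2 differ; both include Days 4, 8, 15, 29 and 43.
3. State a rule for values below quantification on the log scale, since the zero used in SAP 10.1 and 11.1 cannot be logged.
4. Keep the grouped display if wanted, but say that it uses baseline BMI and fix the cut-off before unblinding.
5. Align Protocol 7.4 and 7.5 with the objective, or record the difference in SAP Section 14.

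Cost: no new visits or samples. If all 12 post-dose RVNA visits are modelled, there are 12 × 2 = 24 RVNA fits, plus 3 × 2 = 6 NRG and 5 × 2 = 10 LRG drug fits, or 40 per analysis population before PK parameters. Naming a few RVNA days would reduce this. All of it is descriptive.
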